Based upon the safety results of the BVS Cohort A device, Cohort B of the ABSORB trial was initiated on March 19, 2009 to evaluate Absorb BVS System (mfg MTV), and completed enrollment on November 6, 2009 with 101 subjects split into two groups: Group 1, n=45 (imaging follow-up at 180 days and 2 years) and Group 2, n=56 (imaging follow-up at 1 year and 3 years).

Cohort B is a prospective, open-labeled, multi-center registry that enrolled subjects with up to two *de novo* native coronary artery lesions in separate epicardial vessels with visually estimated nominal vessel diameters of 3.0 mm and lesion(s) length ≤ 14 mm. All subjects in Cohort B received a single 3.0 x 18 mm BVS Cohort B device per lesion treated. The 6-month angiographic results from Cohort B Group 1 demonstrated a late loss of 0.19 mm which is similar to the 0.10 mm late loss of the 3.0 x 18 mm XIENCE V observed in the SPIRIT FIRST trial and compares favorably with the 0.43 mm late loss from Cohort A. At 180 days, the IVUS results from Cohort B Group 1 showed limited intra-scaffold neo-intimal hyperplasia, the volume obstruction (VO) was 1.2% and the neointimal hyperplasia (NIH) area was 0.08 mm². These results compare favorably with XIENCE V in SPIRIT FIRST (VO of 8.0% and NIH area of 0.56 mm²) and with Cohort A (VO of 5.3% and NIH area of 0.29 mm²). As observed in Cohort A, the 6-month IVUS results showed a significant reduction in the average lumen area (6.60 ± 1.22 mm² after procedure vs. 6.37 ± 1.12 mm² at 180-day, p=0.0048). This was much lower than that found for the Cohort A BVS System (6.08± 1.13 mm² after procedure vs. 5.07± 1.22 mm², p=0.0001, at 180-day). The vessel area remained comparable between baseline and 180-day follow-up (14.22 ± 3.75 mm² vs. 14.49 ± 3.67 mm²) demonstrating the absence of negative remodeling.

QCA and IVUS results from baseline, post procedure and 2 year are available for the patients in Cohort B Group 1. The 2-year angiographic results from Cohort B Group 1 demonstrated a late loss of 0.27 mm which compares well to the SPIRIT II XIENCE V 2 year late loss of 0.33 mm. Furthermore, in Cohort B Group 1 (n=33) IVUS data demonstrated lumen, scaffold and vessel enlargement between 6 months and 2 years (**Table 2.3**).

Table 2.3: ABSORB Cohort B Group 1: IVUS Results through 2 Years

	Post-procedure	6 Months	2 years	p-value post vs. 2 years	p-value 6 m vs. 2 years
Average vessel area (mm ²)	14.04 ± 3.80	14.44 ± 3.82	15.35 ± 4.05	< 0.0001	< 0.0001

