5.2 Powered Secondary Endpoint(s)

Imaging Cohort Powered Secondary Endpoints

[REDACTED]

Imaging Cohort Powered Secondary Endpoints are based on the pooled subjects from the Imaging Cohort of Absorb III (■■■■ angiographic subjects and ■■■■ IVUS subjects) and subjects from the Absorb Japan RCT (■■■■ angiographic subjects, and ■■■■ IVUS subjects).

One of the key attributes that differentiates Absorb BVS from metallic stents is the progressive mechanical weakening of the scaffold with polymer degradation over time, which allowed for vessel movement and gradual outward remodeling (positive) to accommodate any increases in the in-scaffold intimal hyperplasia that may limit blood flow. In both the Absorb Cohort A and Cohort B trials, Absorb BVS treated vessels have shown evidence of vessel movement and late lumen and scaffold enlargement, providing anatomic indication that the vessel can adapt and enable the natural Glagov process.²⁴

The vasomotion endpoint assesses the ability of the in-scaffold segment to move when the vessel is no longer mechanically constrained. Angiography will be used for the vasomotion assessment. The assessment of late lumen enlargement will be evaluated by the in-stent/scaffold mean lumen area change (Δ MLA) from post-procedure to 3 years by IVUS.

1. The in-stent/scaffold mean lumen area change, from post-procedure to 3 years by IVUS (mean lumen area measured after nitrate infusions, superiority test, ■■■■ pooled subjects).
2. The in-stent/scaffold mean lumen diameter change, between pre- and post-nitrate infusion at 3 years by angiography (superiority test, ■■■■ pooled subjects).

Powered Secondary Endpoint for Angina

This powered secondary endpoint is intended to assess angina at 1 year and test for superiority of Absorb BVS to XIENCE.

- Angina is defined as the first adverse event resulting in the site diagnosis of angina.
- The analysis will exclude angina following the index procedure through discharge, not to exceed a period of 7 days.

This analysis will include ~2000 subjects.

Powered Secondary Endpoint for All Revascularization

This powered secondary endpoint is intended to assess all revascularization at 1 year and test for superiority of Absorb BVS to XIENCE.

This analysis will include ~2000 subjects.

Powered Secondary Endpoint for Ischemia-Driven Target Vessel Revascularization

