5.3 Additional Secondary Endpoint(s)

In ABSORB III the following clinical secondary endpoints will be analyzed. Secondary imaging endpoints will be analyzed in the Imaging Cohort.

- **Acute Success:** (Combined Clinical/Angiographic Endpoint)
 - Device success (Lesion level analysis)
 - Procedural success (Subject level analysis)
- **Clinical Endpoint** in hospital and at each follow-up point (30 days; 180 days; 1, 2, 3, 4 and 5 years).
 - **Component**
 - Death (Cardiac, Vascular, Non-cardiovascular)
 - Myocardial Infarction
 - Attributable to target vessel (TV-MI)
 - Not attributable to target vessel (NTV-MI)
 - Target Lesion Revascularization (TLR)
 - Ischemia driven TLR (ID-TLR)
 - Non ID TLR (NID-TLR)
 - Target Vessel Revascularization (TVR,)
 - ID TVR
 - Non ID TVR
 - All coronary revascularization
 - **Composite Endpoints**
 - Death/All MI
 - Cardiac Death/All MI
 - Cardiac Death/TV-MI/ID-TLR (TLF)

- Cardiac Death/All MI/ID-TLR (MACE)
- Cardiac Death/All MI/ID-TLR/ID-TVR, non TL (Target Vessel Failure, TVF)
- Death/All MI/All revascularization
- **Scaffold-Thrombosis / Stent Thrombosis (per ARC definition)**
 - Timing (acute, sub-acute, late and very late)
 - Evidence (Definite and Probable)
- **Imaging Endpoints:**

Imaging endpoints will be analyzed on Imaging Cohort subjects only.

- **Angiography:**

All angiographic endpoints will be collected post-procedure and at 3 years

- In-segment²⁵ late loss (LL)
- In-device²⁶ LL
- Proximal LL (proximal defined as 5 mm of tissue proximal to the device placement)
- Distal LL (distal defined as 5 mm of tissue distal to the device placement)
- In-device/in-segment/proximal/distal minimum lumen diameter
- In-device/in-segment/proximal/distal %Diameter Stenosis (DS)
- In-device/in-segment/proximal/distal angiographic binary restenosis
- In-device net gain (change in minimum lumen diameter between 3 years and post-procedure)
- The magnitude of in-stent/scaffold mean lumen diameter change (absolute value) at 3-years follow-up from pre-nitrate to post-nitrate
- The normalized in-stent/scaffold mean lumen diameter change at 3-years follow-up from pre-nitrate to post-nitrate, defined as,

$$\frac{\text{In - Stent/Scaffold Mean Lumen Diameter change}}{(\text{Proximal Mean Lumen Diameter change} + \text{Distal Mean Lumen Diameter change})/2} \times 100\%$$

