²⁵ In-device refers to the margins of the stent or scaffold. Segment refers to the margins of the stent or scaffold and 5 mm proximal and 5 mm distal to the stent or scaffold.

²⁶ Device throughout the protocol summary refers to XIENCE or Absorb BVS System

where both proximal and distal mean lumen diameter changes are at 3-years follow-up from pre-nitrate to post-nitrate

- Change in minimum lumen diameter, within treated segment, at 3 years follow-up from pre-nitrate to post-nitrate
- Change in in-device %DS at 3 years follow-up from pre-nitrate to post-nitrate

○ **IVUS (Grey scale):**

All IVUS endpoints will be collected post-procedure and at 3 years (as applicable) and within the device and within the treated segment:

- Minimal Lumen Area
- Percentage of subjects with late gain without incomplete apposition by IVUS (IVUS minimum lumen area post- procedure post-nitrate - IVUS minimum lumen area 3 years follow-up post-nitrate)
- % change in the tissue area/volume between lumen and external elastic lamina (EEL)
- Absolute change in tissue area/volume between lumen and EEL
- Mean/minimal vessel diameter/area/volume
- Mean/minimal device diameter/area/volume; if analyzable in respect to Absorb BVS
- Mean/minimal lumen diameter/area/volume, including change in minimum lumen area between post-procedure and follow-up
- Mean/maximal neointima hyperplasia area/volume/percentage at 3 years; if analyzable in respect to Absorb BVS
- Incomplete apposition (post-implantation), persisting incomplete apposition, late acquired incomplete apposition and resolved incomplete apposition at 3 years; if analyzable in respect to Absorb BVS

● **OCT:**

All OCT endpoints will be collected post-procedure and 3 years, and for within the device and within the treated segment:

- Descriptive analysis of strut, lesion and vessel morphology
- Mean neointimal area (NIA)
 - Apposed to the vessel wall with neointimal coverage
 - Apposed to vessel wall without neointimal coverage

- Incomplete apposition to vessel wall with neointimal coverage
- Incomplete apposition to vessel wall without neointimal coverage
- Lumen area/volume stenosis %
- Mean/minimal device area
- Mean/minimal luminal area/volume
- Mean strut area/volume
- Persisting incomplete apposition, late incomplete apposition at 3 years (if analyzable)
- OCT analysis for subjects with jailed side branch
- Descriptive analyses from 3-dimensional OCT reconstructions

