10.4.3 Secondary Endpoint Analyses

Secondary endpoints other than the powered endpoints described above will be summarized descriptively for the ITT population. For further details refer to the statistical analysis plan (SAP).

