Re-narrowing of the artery defined as %DS \geq 50%.

ACC/AHA Classification Scheme of Coronary Lesions: Lesion-Specific Characteristics

Type A Lesions (High Success, >85%; Low Risk)

- Discrete (< 10 mm length)
- Concentric
- Readily accessible
- Nonangulated segment, < 45°
- Smooth contour
- Little or no calcification
- Less than totally occlusive
- Not ostial in location
- No major branch involvement
- Absence of thrombus

Type B Lesions* (Moderate Success, 60-85%; Moderate risk)

- Tubular (10-20 mm length)
- Eccentric
- Moderate tortuosity of proximal segment
- Moderately angulated segment, > 45°, < 90°
- Irregular contour
- Moderate-to-heavy calcification
- Total occlusions < 3 mo old
- Ostial in location
- Bifurcation lesions requiring double guide wires
- Some thrombus present

* Type B1 lesions: One adverse characteristic

* Type B2 lesions: ≥ two adverse characteristics

Type C Lesions (Low Success, <60%; High Risk)

- Diffuse (> 2 cm length)
- Excessive tortuosity of proximal segment
- Extremely angulated segments > 90°
- Total occlusions > 3 mo old
- Inability to protect major side branches
- Degenerated vein grafts with friable lesions

CHRONIC OCCLUSION

Total Occlusion:

An occlusion with no antegrade filling of contrast to the distal segment (TIMI grade 0)

Sub-total Occlusion:

TIMI grade 1, and with collateral filling of the distal segment

MAXIMUM DIAMETER (Dmax)

Dmax refers to maximum lumen diameter evaluated after pre-dilatation within the boundaries of intended scaffold segment.

IN-STENT

Within the margins of the stent.

IN-SCAFFOLD

Within the margins of the scaffold.

IN-SEGMENT

Within the margins of the stent or scaffold and 5 mm proximal and 5 mm distal to the stent or scaffold.

LATE LOSS (LL)

General definition: Calculated as MLD post-procedure – MLD at follow-up

- In-segment Late Loss: in-segment MLD post-procedure – in segment MLD at follow-up
- Proximal Late Loss: proximal MLD post-procedure – proximal MLD at follow-up (proximal defined as within 5 mm of healthy tissue proximal to the device placement)
- Distal Late Loss: distal MLD post-procedure – distal MLD at follow-up (distal defined as within 5 mm of healthy tissue distal to the device placement)
- In-device Late Loss: in-device MLD post-procedure – in-device MLD at follow-up

PERCENT DIAMETER STENOSIS [%DS]

The value calculated as $100 * (1 - \text{MLD}/\text{RVD})$ using the mean values from two orthogonal views (when possible) by QCA.

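### The descriptive IVUS late-gain endpoint in ABSORB III is written with the late-loss subtraction, so read literally it counts lumens that shrank

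*Protocol*

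**What the plan says.** Section 5.3 of the ABSORB III part of the protocol, under the grey-scale IVUS endpoints, asks for a responder percentage, specified as: "late gain without incomplete apposition by IVUS (IVUS minimum lumen area post- procedure post-nitrate - IVUS minimum lumen area 3 years follow-up post-nitrate". The expression in brackets is a difference only; no threshold for a responder is given.

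Appendix II, under Late Loss, reads: "General definition: Calculated as MLD post-procedure – MLD at follow-up". Each of the specific late-loss measures listed there has the post-procedure term first and the follow-up term second.

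The powered imaging endpoint is a different quantity. Section 5.2 states: "The assessment of late lumen enlargement will be evaluated by the in-stent/scaffold mean lumen area change", and lists it as "The in-stent/scaffold mean lumen area change, from post-procedure to 3 years by IVUS". It uses mean rather than minimum lumen area, is continuous, and carries no condition on apposition.

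On inferential status, section 10.4.3 says: "Secondary endpoints other than the powered endpoints described above will be summarized descriptively for the ITT population". The SAP supplied with the protocol covers ABSORB IV only (SAP section 1.1), so it neither restates nor corrects this ABSORB III endpoint.

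**The concern.** The protocol gives one order of subtraction two opposite names. In Appendix II, post-procedure minus follow-up is a loss; in the section 5.3 IVUS list, the same order is a gain. Only the Appendix II usage fits the ordinary meaning of the words and the protocol's own account of late lumen enlargement, which is growth over time.

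A sign error is easier to miss in a percentage than in a mean. A continuous change reported with the wrong sign tends to be noticed, but a responder rate has no sign to check. If the bracketed formula were programmed as printed and positive values counted, shrunken lumens would be tabulated as successes, and the arm with more true enlargement would usually look worse on this line.

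**Working it through.** The plan attaches no sample size, power or alpha to this endpoint, so there is no stated figure to reproduce. Two checks apply.

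**1. Direction, on the protocol's own lumen areas.** These are average lumen areas from section 2.1.9, not minimum lumen areas at 3 years, so they test only the sign of the formula.

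| Source | Post-procedure (mm²) | Follow-up (mm²) | As printed: post minus follow-up | Follow-up minus post |
|---|---|---|---|---|
| Cohort A, 180 days | 6.08 | 5.07 | +1.01 | -1.01 |
| Cohort B Group 1, 2 years (Table 2.3) | 6.53 | 6.85 | -0.32 | +0.32 |

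The Cohort A row comes from "6.08± 1.13 mm² after procedure vs. 5.07± 1.22 mm²", which the text describes as a reduction. The printed formula gives it a positive value. Cohort B Group 1, where the mean rose, gets a negative one. Follow-up minus post-procedure gives the sign that the word gain requires in both rows.

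**2. Effect on the arm comparison, under assumptions.** The documents give no arm means, SD or rates of incomplete apposition for this endpoint, so all are assumed. Let the change (3-year minus post-procedure) be Normal with mean m and standard deviation s, and call a subject a responder if the computed value exceeds zero.

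- Correct order: responder share g = Φ(m/s).
- Printed order: responder share 1 - g.

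With m = +0.32 mm² in one arm and -0.20 mm² in the other, and s = 1.0 mm²:

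- Correct: Φ(0.32) = 62.6% versus Φ(-0.20) = 42.1%, a difference of +20.5 points.
- Printed: 37.4% versus 57.9%, a difference of -20.5 points.

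For the same means, s = 0.8 gives +25.4 against -25.4 and s = 1.5 gives +13.8 against -13.8. With smaller means (+0.20 and 0.00) and s = 1.0, the pair is +7.9 against -7.9. Without the apposition condition, the difference always turns into its exact negative.

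**3. The apposition condition.** Suppose shares qT and qC of the two arms have incomplete apposition, independent of the change, and cannot be responders. The difference is then gT(1 - qT) - gC(1 - qC) in the correct order and (1 - gT)(1 - qT) - (1 - gC)(1 - qC) as printed. With s = 1.0:

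| Assumed means (mm²) | qT, qC | Correct (points) | As printed (points) | Reversed? |
|---|---|---|---|---|
| +0.32, -0.20 | 5%, 5% | +19.5 | -19.5 | yes |
| +0.32, -0.20 | 5%, 15% | +23.7 | -13.7 | yes |
| +0.32, -0.20 | 2%, 30% | +31.8 | -3.8 | yes |
| +0.32, -0.20 | 0%, 40% | +37.3 | +2.7 | no |
| +0.20, 0.00 | 5%, 15% | +12.5 | -2.5 | yes |
| +0.20, 0.00 | 2%, 30% | +21.8 | +6.2 | no |

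An imbalance the other way can also prevent a reversal. With 40% and 0% and the first pair of means, the correct order gives 0.626 × 0.60 - 0.421 = -0.045 and the printed order gives 0.374 × 0.60 - 0.579 = -0.355, both negative. Reversal is therefore the expected result when apposition is similar in the two arms, but it is not an identity.

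**The case against.** The strongest reply is that little depends on this line, and most of that reply stands.

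- **The label claim.** A reader might infer that the claim of superiority for late lumen enlargement is at risk. The documents do not support that. The Study Design entry of the Protocol Summary ties the claim to the powered secondary endpoint data, and section 5.2 assigns late lumen enlargement to the mean lumen area change. No text presents the responder percentage as a version of that claim. Nor would a reversed percentage strictly contradict the powered result, because minimum and mean lumen area are different measures.
- **Certainty of the reversal.** No cut-off is printed, and the words of the endpoint say gain. An analyst who follows the label rather than the brackets would get it right. The same IVUS list also calls for minimal lumen area at each time and for its change, so a reversed percentage could be caught against the neighbouring tables.
- **Net gain.** A reader might see a second fault in "In-device net gain (change in minimum lumen diameter between 3 years and post-procedure", among the angiographic endpoints. That text prints no subtraction order, and its natural reading, 3 years less post-procedure, has the right sign for a gain. Overlap with in-device late loss is redundancy, not error.
- **The missing SAP.** Section 10.4.3 refers to a SAP for detail. The ABSORB III SAP was not available and may state the sign and the cut-off.

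None of this repairs the printed formula. An endpoint whose definition is right only if its own formula is ignored still needs correcting, and if the ABSORB III SAP already has the right sign, the protocol disagrees with it.

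**Conclusion.** The formula for the late-gain responder endpoint is wrong as written: it is the protocol's late-loss subtraction under the name of gain, and nothing in the supplied documents corrects it. Taken literally, with positive values counted as gain, it counts subjects whose minimum lumen area fell. The arm comparison on this endpoint would then be expected to reverse, by 20.5 points in each direction in the main illustration, unless incomplete apposition differs strongly between arms.

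The sign finding rests on the text alone. The size rests on assumed means, SDs and apposition rates, on normality, and on a cut-off of zero that the protocol does not state. The consequence is limited to one descriptive endpoint in the imaging cohort. It is a minor correction to a definition; no powered test, alpha allocation or label claim depends on it.

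**What to change.** In section 5.3 of the ABSORB III protocol, define late gain as the IVUS minimum lumen area at 3 years minus the IVUS minimum lumen area post-procedure, both measured post-nitrate, and state the responder cut-off, for example a value greater than zero. Keep the apposition condition as a separate clause, so that it is clear which subjects it removes from the numerator. Check that the ABSORB III SAP and the analysis program use the same order and cut-off.

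The cost is one line in the protocol and a matching line in the ABSORB III SAP. It needs no new data, no added imaging and no change to sample size. The angiographic net-gain endpoint needs no correction on this ground.

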5.4 Informational Endpoints (Patient Reported Outcomes)

In the 2000 primary analysis subjects of ABSORB III the following Patient Reported Outcomes will be analyzed as informational endpoints.

- Overall Health Status in hospital (baseline) and at the specified follow-up contacts (30 days; 1, 2, 3 and 5 years) assessed using the EuroQoL 5D (EQ-5D)
- Disease-Specific Quality of Life in hospital (baseline) and at the specified follow-up contacts (30 days; 1, 2, 3 and 5 years) assessed using the Seattle Angina Questionnaire (SAQ)
- Dyspnea severity in hospital (baseline) and at the specified follow-up contacts (30 days; 1, 2 and 3 years) assessed using the Rose Dyspnea Scale (RDS)
- Anxiety in hospital (baseline) and at the specified follow-up contacts (30 days; 1, 2 and 3 years) assessed using the Generalized Anxiety Disorder scale (GAD-7)

6. SUBJECT SELECTION AND WITHDRAWAL

6.1 Subject Population

Subjects registered into this Clinical Investigation will be male and female subjects derived from the general interventional cardiology population. The Clinical Investigation will register approximately 2250 subjects, with a maximum of two *de novo* native coronary artery lesions in separate epicardial vessels, who meet all eligibility criteria, have provided written Informed Consent and have been registered in the trial.

6.2 Subject Screening and Informed Consent

6.2.1 Subject Screening

Subjects planned to be admitted for a percutaneous coronary artery revascularization procedure should be screened for Clinical Investigation eligibility by a member of the research team previously trained to the Clinical Investigation Plan.

Subjects that have signed an Informed Consent (Refer to **Appendix IV**, Enrollment and Registration Process) are considered enrolled in ASBORB III. Subjects who do not satisfy the general angiographic inclusion and exclusion criteria and/or have unsuccessful pre-dilatation and/or vessel sizing are considered screen failures and will not proceed further in the trial. These subjects will be entered into the eCRF screening log (as applicable; in addition, the reason for screen failure as well as supporting data will be entered into the log).

6.2.2 Informed Consent

The Investigator or designee, who has been trained on the protocol, will explain the nature and scope of the trial, potential risks and benefits of participation, and answer questions for the subjects. All subjects (or legally authorized subjects' representatives, if applicable) must sign and date the Institutional Review Board (IRB) /Medical Ethics Committee (MEC) approved informed consent prior to any clinical trial/investigation-specific procedures. No patients belonging to a vulnerable population will be enrolled. Vulnerable population is defined as subject whose willingness to volunteer in a clinical investigation could be unduly influenced by the expectation, whether justified or not, of benefits associated with participation or of retaliatory response from senior members of a hierarchy in case of refusal to participate. Examples of populations which may contain vulnerable subjects include: Individuals with lack of or loss of autonomy due to immaturity or through mental disability, persons in nursing homes, children, impoverished persons, subjects in emergency situations, ethnic minority groups, homeless persons, nomads, refugees, and those incapable of giving informed consent. Other vulnerable subjects include, for example, members of a group with a hierarchical structure such as university students, subordinate hospital and laboratory personnel, employees of the sponsor, members of the armed forces, and persons kept in detention.

Obtaining of the consent, provision of a copy to the subject, along with the date must be documented in the subject's medical records. The informed consent form must be signed by an investigator or designate trained on the protocol. In addition, the signed informed consent must be kept in the subject's medical records/research chart and a copy must be given to the subject or the legally authorized representative.

In addition, an authorization for use and disclosure of the subjects' protected health information, in accordance with the Health Insurance Portability and Accountability Act (HIPAA), must be obtained from the subject or their legally authorized representative (US only).

For Live cases at congresses the patients need to sign a specific Live Case ICF, approved by the IRB/EC and by Abbott Vascular, as well as by the competent authorities (e.g., FDA), as applicable. The investigator must request Abbott Vascular approval prior to, performing a Live Case.

